Primary specific aim: *To test the dose-related effects of ketamine on PTSD symptoms in the Veteran and active duty military populations.* In this 2-site study, approximately 198 eligible Veterans and active duty personnel who meet criteria for PTSD and the additional inclusion and exclusion criteria (detailed in Section III-A) will be randomized to one of three treatment arms (placebo, ketamine 0.2 mg/kg, ketamine 0.5 mg/kg). Participants will receive the study drug or placebo via intravenous infusion twice per week for 4 weeks. The primary outcome measure will be the PTSD Checklist (PCL-5). Data will be stratified by site (Texas vs. Connecticut) and by the presence of comorbid mild-to-moderate alcohol dependence. A random effects/mixed model will be applied to the data. The study is powered based on the effect size of ketamine in the Mount Sinai study to detect a significant interaction of ketamine dose and time during this trial.

Secondary specific aims:

1. Safety of repeated ketamine exposure: We will evaluate the safety of ketamine exposure in the following ways: (1) induction and persistence of psychotic and dissociative symptoms will be evaluated during ketamine infusion, prior to discharge at each ketamine test day, and at two weeks and one month following the last ketamine infusion; (2) breath alcohol levels will be evaluated prior to randomization, throughout the trial, and for 4 weeks following the last ketamine exposure; (3) medical and psychiatric adverse events and serious adverse events will be recorded following FDA, VA Cooperative Studies Program, and Consortium for the Alleviation of PTSD (CAP) guidelines.

2. Durability of benefit: Following completion of the randomized testing, psychometric ratings (PCL-5 and other outcome measures) and safety assessments will be obtained on a weekly basis for 4 weeks to qualitatively and quantitatively characterize (random effects model covarying for end-of-treatment severity) the dose-related durability of benefit in responders to the randomized treatment.

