Blood collection and banking justification: Several biomarkers have been linked to the rapid antidepressant effects of ketamine, e.g. the lower activity “Met” allele of the Val66Met BDNF gene polymorphism show poorer antidepressant responses to ketamine and changes in plasma BDNF levels correlated with treatment response.⁵⁹⁻⁶² Additionally, ketamine has known anti-inflammatory effects that were recently linked to its antidepressant effects in some preclinical

models 63. The blood collection and banking at the CAP Biomarkers and Genomics Core (San Antonio, TX) will be used to investigate the relationship between ketamine effects on PTSD symptoms and the following blood biomarkers: 1. Val66Met BDNF gene polymorphism; 2. BDNF level, 3. S100B, and 4. Inflammatory markers (TNF α , IL-1b, IL-6, IL-1).

Table 2.

ASSESSMENT / PROCEDURE	VISIT 1	VISIT 2	VISIT 3	VISITS 4-6 ; 8-10	VISIT 7	VISIT 11	VISIT 12	OL FU (post-8th INF/Vst 12.5)	VISITS 13-15	VISIT 16
	SCR	INFUSION 1	FU 1	INF 2,3,4,6,7,8	INFUSION 5	FU 2	FU 3 - OPTIONAL VISIT OPEN LABEL (post-8th infusion)	OL FU	FUs 4-6	FU 7
		DAY 0	DAY 1	DAYS 3, 7, 10, 17, 21, 24	DAY 14	DAY 25	28	29	DAY 35, 42, 49	DAY 56
Adverse Events		X (PRE INF)	X	X (PRE INF)	X (PRE INF)	X	X (PRE INF)	X	X	X
AUDIT	X									
ARAC		X (30, 120)	X	X (30, 120)	X (30, 120)	X	X (30, 120)	X	X	X
B-IPF	X		X					X	X	X
CGI		X (PRE INF)	X	X (PRE INF)	X (PRE INF)	X	X (PRE INF)	X	X	X
CADSS		X (30, 120)		X (30, 120)	X (30, 120)		X (30, 120)			
CAPS-5	X					X				X
Concom Med Log	X	X	X	X	X	X	X	X	X	X
Demographics & Military Service	X									
DRRI-2 - Combat	X									
DRRI-2 - Post-Battle	X									
DSI-SS	X	X	X	X	X	X	X	X	X	X
FTND	X		X			X		X	X	X
FTND-ST	X		X			X		X	X	X
GAD-7		X (PRE INF)	X	X (PRE INF)	X (PRE INF)	X	X (PRE INF)	X	X	X
Health Interview	X									X
History of Head Injury (DVBIC)	X									X
Informed Consent*	X									
ISI		X (PRE INF)	X	X (PRE INF)	X (PRE INF)	X	X (PRE INF)	X	X	X
LEC-5	X									X
MGH-ATRQ	X									
MINI-7	X									
MADRS - Full Scale		X (PRE INF)	X	X (PRE INF)	X (PRE INF)	X	X (PRE INF)	X	X	X
MADRS - Item 10 Only	X									
NRS-Pain	X		X			X		X	X	X
PHQ-9	X					X				X
PROMIS (Sleep)	X		X			X		X	X	X
PANSS		X (30, 120)		X (30, 120)	X (30, 120)		X (30, 120)			
PCL-5	X	X (PRE INF)	X	X (PRE INF)	X (PRE INF)	X	X (PRE INF)	X	X	X
PGI		X (PRE INF)	X	X (PRE INF)	X (PRE INF)	X	X (PRE INF)	X	X	X
QDS	X	X			X	X			X (14 only)	X
QIDS-SR	X	X (PRE INF)	X	X (PRE INF)	X (PRE INF)	X	X (PRE INF)	X	X	X
STBI	X					X				X
STOP	X									

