Sample size justification: Murrough et al. reported large effect sizes (all d 's > 1.42) in a study of open-label repeated doses of ketamine for depression.²¹ In the recent study of a single infusion of ketamine in PTSD,²⁷ there was a medium effect size (Cohen's $d=0.6$) for the comparison between change in PTSD symptoms on ketamine and midazolam from baseline to 24 hours post-infusion. In our study, we expect that the effect size for the comparison between the higher dose ketamine vs. lower dose ketamine will be similar (i.e. Cohen's $d=0.6$). Furthermore, the effect size for the comparison between the higher dose ketamine and placebo is expected to be much larger (effect size of at least $d=0.8$) since response on placebo will be smaller than response on an active comparator and our trial has significantly longer duration than the Feder et al. study. This effect size is still much smaller than the estimated effect sizes for the corresponding comparison in subjects with major depression observed by Murrough et al.²¹ Based on the effect sizes for the individual comparisons, the expected effect size for the overall treatment by time interaction is medium (Cohen's $f=0.24$). Thus we estimate that we need 53 subjects per group to test the

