primary hypotheses with at least 80% power at two-sided alpha level of 0.05. In particular, with 53 subjects per group we have 87% power to detect a treatment by time interaction of magnitude $f=0.24$ and 80% power to detect pairwise differences of magnitude $d=0.6$ or higher at two-sided alpha level of 0.05. Holm-Bonferroni adjustment will be used for the pairwise comparisons and is taken into account in the power calculation so that the family-wise error rate for the pairwise comparisons is kept at 0.05 level. Testing of between group differences over time will be performed within the mixed effects models which are expected to be even more powerful since they use all available data on each individual including data on subjects who dropout or have intermittent missing data due to non-compliance with the treatment schedule. To address potential limitations related to the external validity, we have expanded the age range (18-70), included active duty military personnel and non-OEF/OIF/OND Veterans, and will use stratified randomization to match and balance on study site and alcohol use comorbidity during the trial. Additionally, we plan to track participant duty status, years since trauma and treatment history, and examine these factors in post-hoc analyses.

Analysis plan: Descriptive statistics will be calculated prior to statistical analysis. Distributions of quantitative variables will be assessed for normality using normal probability plots and Kolmogorov-Smirnov statistics and transformations or non-parametric methods will be used as necessary. All statistical tests will be two-sided. Uncorrected alpha level of 0.05 will be used for testing the primary hypothesis as described below. Pairwise post-hoc comparisons and tests of secondary outcome measures will be adjusted using Holm-Bonferroni procedure. Randomized treatment groups will be compared at baseline on potentially confounding factors (e.g. age, sex, history of substance abuse) and variables that are significantly different between groups will be included as additional covariates in the models below. All analyses will be intent-to-treat.

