Primary specific aim: To test the dose-related effects of ketamine on PTSD symptoms in Veterans and active duty military population. We will follow our prior PTSD clinical trial,⁵ using mixed effects regression models, with group, time, group by time effects for the primary outcome variable (PCL-5). We will stratify by infusion center and alcohol use comorbidity. We do not expect to observe significant differences in treatment effects by infusion center but we will test the interaction of treatment group and infusion center and perform follow-up analyses by site as necessary. Similarly, we do not expect significant moderating effects of alcohol use comorbidity but will assess the interaction between treatment and alcohol use comorbidity and perform follow-up tests as necessary. This approach will be applied to most secondary outcome measures as well. Mixed effects regression models use all available data on each subject, are flexible in modeling the correlation structure of the data and give unbiased results under missing at random assumptions. We will select the best-fitting correlation structure for the primary and each secondary outcome based on Schwarz-Bayesian Information Criterion (BIC). Time will be considered as a categorical predictor and post-hoc tests between groups will be conducted for the change from baseline to end-point, which is of primary interest. To assess the trajectory of ketamine effects over time, we will test for linear, quadratic and higher order time trend differences. Post-hoc tests will also be performed to assess whether dose effects are linear. Change in PTSD symptoms is expected to be the largest for the higher dose ketamine group. However, it is possible that the change in the higher dose ketamine group is not significantly different from the change in the lower dose ketamine group. Thus, we will also estimate effect sizes with confidence intervals for the change from baseline to end-point in each group and use this information together with safety data to inform dose selection for potential future studies of ketamine efficacy and evaluation of mechanism of action in PTSD.

In addition to testing the potential moderating effect of comorbid alcohol use described above, we will also perform exploratory analyses to assess moderating effects of depression, medication

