## Supplemental

Mixed models were constructed to evaluate the effects of posttraumatic stress disorder (PTSD) treatment on the PTSD Checklist for DSM-5 (PCL-5), Clinician-Administered PTSD Scale for DSM-5, Montgomery-Asberg Depression Rating Scale (MADRS), Clinician-Administered Dissociative State Scale (CADSS), and Positive and Negative Syndrome Scale (PANSS) based on all available observations within individual patients. Treatment group (Standard, Low, Placebo), time (pre each infusion, 24 hours post-first and post-last infusions for PCL-5 and MADRS, baseline and post-last infusion for CAPS-5, during each session for CADSS and PANSS), site and all possible interactions were fit as fixed effects. Alcohol use disorder (AUD) diagnosis was included as a covariate. The CADSS and PANSS models also included interval (30 and 120 minutes) and the interaction between interval and treatment. Subject was the clustering factor. The best-fitting variance-covariance structure in each model was selected based on Bayesian information criterion. Residuals were assessed, and CADSS was logtransformed to correct for positive skewness of this outcome. In the final models, nonsignificant interactions not involving treatment were dropped for parsimony. Focused least square mean comparisons of change from baseline to 24 hours post-first infusion and from baseline to 24 hours post-last infusion within treatment group, and for pairwise differences in change from baseline between treatment groups, were evaluated regardless of the significance of the interactions and main effects. Follow-up data on the PCL-5 and CAPS-5 also were analyzed using mixed models covarying for baseline severity. Individuals with open label treatment were excluded from these analyses. Responder status was calculated as at least 25% improvement from pretreatment on the PCL-5. Missing data were treated as failure (i.e., nonresponder). The primary analyses for the binary outcomes were logistic regressions with treatment, site, and AUD as predictors, and missing treated as failure. The treatment by site interactions were nonsignificant and were dropped for parsimony in the final models.

For the PCL-5 self-assessments, 1.6% of assessments specified incorrect index trauma event referenced for symptom scoring, and 23.6% of assessments were completed without specifying the index trauma. A sensitivity analysis determined that mixed methods ANOVA results were essentially unchanged with or without their inclusion.

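### Does the 87% power for the treatment-by-time interaction fail once all ten PCL-5 time points are counted?

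*Protocol*

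**What the plan says.** The protocol's primary specific aim says the study is powered "to detect a significant interaction of ketamine dose and time during this trial". The sample size justification (section IV.F) assumes d=0.6 for higher against lower dose and at least d=0.8 for higher dose against placebo. It continues: "Based on the effect sizes for the individual comparisons, the expected effect size for the overall treatment by time interaction is medium", with f=0.24. It then concludes that 53 subjects per group allow a test of the "primary hypotheses with at least 80% power at two-sided alpha level of 0.05", and that "with 53 subjects per group we have 87% power to detect a treatment by time interaction of magnitude" f=0.24.

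On the test itself, the analysis plan states: "Uncorrected alpha level of 0.05 will be used for testing the primary hypothesis as described below". Under the primary specific aim in the same section: "Time will be considered as a categorical predictor and post-hoc tests between groups will be conducted for the change from baseline to end-point"; that change is named as the main interest. The SAP (Supplemental) lists the times in the model: "pre each infusion, 24 hours post-first and post-last infusions for PCL-5 and MADRS". Table 2 of the protocol agrees. It has Day 0, Day 1, "DAYS 3, 7, 10, 17, 21, 24" for infusions 2-4 and 6-8, Day 14 for infusion 5, and Day 25.

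**The concern.** Eight pre-infusion assessments plus two 24-hour assessments make ten time points. With three groups and categorical time, the interaction has (3-1)×(10-1)=18 df. The effect sizes in the power paragraph, however, describe a single change from baseline. If the noncentrality from that one contrast is spread over 18 df, power drops below the 80% target.

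The stake is real in principle. The protocol's Significance section ties the decision to continue development to p≤0.05 in the primary analysis. An omnibus test with too little power could miss a true end-point benefit that a focused contrast would very probably detect.

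**Working it through.** **Inputs from the documents.** 53 per group (N=159), two-sided alpha 0.05, d=0.6 and d=0.8, f=0.24, ten time points. Correlations and trajectories are not stated; every one used below is an assumption.

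**Where f=0.24 comes from.** Setting the placebo change to 0, the d values give group changes of 0, 0.2 and 0.8 in SD of change, with mean 0.333. Their root-mean-square spread is √[(0.1111+0.0178+0.2178)/3] = 0.340, and 0.340/√2 = 0.240. So f=0.24 matches the end-point effects on a two-time-point scale.

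**Noncentrality of the end-point contrast.** λ = 53×(0.1111+0.0178+0.2178) = 53×0.3467 = 18.37. The two-time-point form agrees: 2×159×0.24² = 18.32.

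**Power if λ stays at 18.37.** Noncentral F with df1 = 2(m-1). The denominator df is 2(N-3-(m-1)+2) (multivariate) or (N-3)(m-1) (mixed model).

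| Time points m | df1 | Power, multivariate | Power, mixed model |
|---|---|---|---|
| 2 | 2 | 97.6% | 97.5% |
| 5 | 8 | 87.7% | 88.2% |
| 8 | 14 | 78.1% | 79.5% |
| 10 | 18 | 72.4% | 74.5% |

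**Can the printed 87% be reproduced?** It can be reached, but the stated inputs do not determine it. Five time points with fixed λ comes close. So does a one-way ANOVA with f=0.24 on all 198 randomised (86.0%). A ten-time-point repeated-measures calculation with the lower-bound sphericity correction and correlation 0.15 gives 87.6%. If f=0.24 is itself held at ten time points under sphericity, power exceeds 99%. Nothing in the documents selects one of these routes.

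**Why 18.37 is a floor.** The interaction tests nine change contrasts jointly, and the baseline-to-end-point change is one of them. The joint noncentrality cannot be smaller than that of any single contrast. It equals 18.37 only when the other visits add nothing.

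**Noncentrality with ten visits.** Let v hold the between-group change at each visit, as a fraction of the end-point change and scaled by the SD of that change. Let V be the covariance of the ten scores and C the matrix of changes from baseline. Then λ = 18.37 × v′(CVC′)⁻¹v. With 53 per group:

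| Assumed correlation and trajectory | λ | Power at 18 df |
|---|---|---|
| AR(1) 0.9 per visit, linear over visits | 18.4 | 72-75% |
| AR(1) 0.97 per day, linear over days | 18.4 | 72-75% |
| Compound symmetry 0.5, half effect at every visit before Day 25 | 18.4 | 72-75% |
| AR(1) 0.9 per visit, linear over days | 20.7 | 79-81% |
| AR(1) 0.97 per day, linear over visits | 22.2 | 82-84% |
| Compound symmetry 0.5, full effect at Days 1 and 25, half before infusions | 26.6 | 90-92% |
| Compound symmetry 0.5, linear over days | 46.9 | over 99% |

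The three low rows are not three pieces of evidence. In each, trajectory and correlation are matched so that λ falls back to the floor. Changing only the time scale of the ramp moves power to 79-84%.

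**Which pattern fits the protocol best?** The d=0.6 comes from a comparison 24 hours after a single infusion. The ketamine regimen justification reports symptoms rising again between days 3 and 7. Both point to larger effects at the 24-hour visits than before the next infusion, which is the 90-92% row.

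**Two further conservative choices in the floor.**
- It counts completers only. The analysis is intent-to-treat on about 66 per group. With complete data on all of them, λ = 66×0.3467 = 22.88 and power is 84-86%. That is an upper bound for the floor case, since dropouts contribute only part of their data.
- It takes d=0.8 exactly, although the protocol calls it a minimum. Keeping d=0.6 between doses, d=0.9 against placebo gives λ = 22.3 and 83-84%, still with no information from intermediate visits.

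**The case for a change.** The strongest case for action is that the stated inputs secure 80% power for the end-point change but not for the 18-df interaction that carries the 0.05. The floor also occurs under two common covariance families, so it is more than a curiosity. The protocol says the mixed model should be more powerful because it uses all available data, but it does not quantify the gain. On this view the power should be recomputed with stated inputs and, if it falls short, the 0.05 moved to the end-point contrast.

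Two parts of this stand. The power paragraph omits the inputs needed to check its figure, and 80% is not guaranteed under every trajectory.

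The rest does not lead to a change. Choosing between the omnibus and the end-point test is a trade-off. The end-point contrast has about 97% power whatever the path. The omnibus test does better under some paths (over 99% for a linear build-up with compound symmetry) and picks up effects that are not confined to the last visit. The end-point comparison is not hidden behind the interaction either, because the SAP evaluates the focused contrasts whether or not the interaction is significant. The Significance section says what a positive result would support; it sets no rule that a missed omnibus test ends development. Finally, the SAP is written in the past tense and already describes results, so there is no evident window before unblinding in which to rename the primary test.

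**Conclusion.** No change to the plan is called for. The ten time points, the 18 df and the arithmetic are correct, but 72-75% is the least favourable value and should not be read as the power of the planned test. It requires intermediate visits that add nothing, exactly 53 completers per group with no contribution from dropouts, and d exactly 0.8. Relaxing any one of these raises power. In the cases computed, power at ten visits runs from 72-75% to over 99%, and the pattern nearest the protocol's rationale gives 90-92%, at or above the printed 87%. These figures rest on assumed correlations and trajectories, because the documents give none.

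The check shows neither that the 87% was miscalculated nor that the planned test misses 80%. What is left is missing detail: the time points, degrees of freedom, correlation and derivation of f=0.24 are not written down. Supplying them would make the figure checkable, but would alter neither the enrolment target nor the model or the contrasts the SAP reports.

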Across both sites, we anticipate recruiting, consenting, and screening approximately 240 male and female Veteran and active duty military subjects (~120/site), between the ages of 18-70 years, in order to meet the target enrollment goals. In order to account for subject drop outs and the potential need to discontinue subjects before study completion (see below for discontinuation criteria) and retain a sample of ~159 subjects completing the double-blind treatment phase (~53 per treatment group), approximately 198 eligible subjects (~66 in each group) who meet criteria for PTSD as determined by the Clinician Administered PTSD Scale (CAPS-5) and the study inclusion criteria outlined below, will be randomized.

At the West Haven VA, we intend to randomize approximately 99 Veteran and active duty military personnel. In order to account for subject dropouts and the potential need to discontinue subjects before study completion (see below for discontinuation criteria) and retain a sample of at least ~80 subjects completing the double-blind treatment phase, approximately 120 eligible subjects (see below for eligibility criteria), will be randomized into the study.

B. Inclusion and Exclusion Criteria:

Inclusion Criteria:

1. Male or female Veterans and active duty military personnel between the ages of 18-75 years seeking treatment for PTSD.
2. Diagnosis of PTSD with a score of 23 or higher (i.e. severe PTSD) on the Clinician-Administered PTSD Scale (CAPS-5) at screening.

3. Treatment resistance to at least one adequate trial of an antidepressant as determined by the Massachusetts General Hospital Antidepressant Treatment History Questionnaire (MGH-ATRQ).
4. Subjects on prescribed nicotine replacement therapy (i.e. patch/lozenge) may enter the study and continue the prescribed nicotine treatment for the duration of their participation. Should the participant plan to use their nicotine replacement therapy during infusion visits, it is asked that they bring in the original packaging with the prescription label on it.
5. Subjects on FDA-approved antidepressant, trazodone, atypical neuroleptic, prazosin, or clonidine may enter the study if they have been on an overall stable treatment, as determined by the study clinician, for at least 4 weeks prior to randomization. Following randomization, changes to doses may be allowable at the investigator's discretion.

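### Holm-Bonferroni on the three pairwise arm comparisons is valid but needlessly strict at its second step; Shaffer's version would gain about 5 points of power for high versus low dose at no cost in error rate

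*Protocol*

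**What the plan says.** Protocol section IV.F, Sample size justification, plans 53 subjects per group and states "80% power to detect pairwise differences of magnitude $d=0.6$ or higher at two-sided alpha level of 0.05". It adds that "Holm-Bonferroni adjustment will be used for the pairwise comparisons and is taken into account in the power calculation". The Analysis plan in the same section repeats the rule: "Pairwise post-hoc comparisons and tests of secondary outcome measures will be adjusted using Holm-Bonferroni procedure". It also says "All statistical tests will be two-sided".

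On effect sizes, the justification says "we expect that the effect size for the comparison between the higher dose ketamine vs. lower dose ketamine will be similar" (d = 0.6), and puts high dose versus placebo at 0.8 or more. Section IV.A gives about 53 completers per group out of about 66 randomized. The Primary specific aim paragraph makes the between-group change from baseline to end-point the quantity of main interest, allows that the two doses may not differ significantly, and says the effect estimates will help inform dose selection.

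The SAP (Supplemental) evaluates the pairwise differences in change whatever the interactions and main effects show. It names no multiplicity adjustment.

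**The concern.** The three pairwise nulls are linked: high minus placebo equals high minus low plus low minus placebo. If one equality fails, the other two cannot both hold. Plain Holm ignores this and, after one rejection, still divides 0.05 by two, as if two true nulls could remain.

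The power given up falls largely on high versus low dose, the contrast that carries the assumed 0.6 and bears on the dose-related primary aim. The pairwise contrasts are not gated by the overall test in the SAP, so nothing else in the plan recovers the lost efficiency.

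**Working it through.** **Inputs.** From the protocol: n = 53 per group, or 66 if all randomized subjects counted; d = 0.6 for high versus low; d of at least 0.8 for high versus placebo; two-sided family-wise 0.05. Derived: low versus placebo = 0.8 − 0.6 = 0.2 on a common SD. Assumed: normal change scores with SD 1 in each arm, and no gain from repeated measures or from dropouts' partial data.

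**Step 1: reproduce the stated 80%.** Power ≈ Φ(d√(n/2) − z), where z is the two-sided critical value. Here d√(n/2) = 0.6 × √26.5 = 3.089.

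| Two-sided level | z | Power (normal) | Power (noncentral t) | n per group for 80% |
|---|---|---|---|---|
| 0.05/3 = 0.0167 | 2.394 | 75.6% | 74.3% | 59 |
| 0.05/2 = 0.025 | 2.241 | 80.2% | 79.1% | 53 |
| 0.05 | 1.960 | 87.1% | 86.4% | 44 |

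Only 0.025 reproduces both the 80% and the 53. The stated power is therefore the power at Holm's second step, with one other pair already rejected and the third not.

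**Step 2: the logical restriction.** Among three pairwise equalities, the number of true ones can be three, one or none, but never two. Holm's thresholds are 0.0167, 0.025, 0.05. Shaffer's are 0.0167, 0.05, 0.05. Each is at least as large as Holm's, so every Holm rejection is kept.

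**Step 3: family-wise error of Shaffer's steps.**
- All three nulls true: an error needs the smallest p-value to be at most 0.05/3, so the Bonferroni bound gives at most 5%. Simulated: 4.3 to 4.4%.
- Exactly one null true: an error needs that one p-value to be at most 0.05, so at most 5%. Simulated: 4.9 to 5.0%. Holm uses only about 3.5% here.
- Exactly two nulls true: impossible.

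**Step 4: power of the full procedures.** Simulated with pooled-SD t tests, 53 per arm (df = 3 × 53 − 3 = 156), at least 200,000 replicates per pattern. Means are placebo/low/high in SD units.

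| Means | Contrast | Holm | Shaffer | Gain (points) |
|---|---|---|---|---|
| 0/0.2/0.8 (expected) | high vs low (0.6) | 80.5% | 85.7% | 5.2 |
| 0/0.2/0.8 | high vs placebo (0.8) | 95.9% | 96.5% | 0.6 |
| 0/0.2/0.8 | low vs placebo (0.2) | 15.3% | 17.6% | 2.3 |
| 0/0/0.6 or 0/0.6/0.6 | each true 0.6 difference | 77.7–77.9% | 81.8–81.9% | 4.0 |
| 0/0/0.6 or 0/0.6/0.6 | both true differences | 68% | 76% | 8 |
| 0/0.3/0.6 | high vs placebo (0.6) | 75.5% | 76.4% | under 1 |
| 0/0.3/0.6 | each adjacent 0.3 difference | 25% | 32% | 7 |
| 0/0.6/1.2 | high vs low (0.6) | 86.0% | about 86.5% | 0.5 |

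In 0/0/0.6 the true differences are high versus low and high versus placebo. In 0/0.6/0.6 they are the two placebo contrasts.

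**Step 5: 66 per arm.** If every randomized subject contributed fully, which is an upper bound, high versus low in the expected pattern goes from 89.6% to 92.7%, a gain of 3.1 points.

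**The case against.** The strongest reply is that nothing here is broken. Holm is prespecified and controls the family-wise error. The primary hypothesis is the treatment-by-time interaction at uncorrected 0.05 with 87% stated power, and the pairwise contrasts are called post-hoc. About 66 per arm are randomized, and the mixed model uses partial data, so real power may exceed the 53-per-arm figures. All of this stands. It makes the change an optional efficiency gain and not the repair of an error.

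Two stronger readings are tempting, and the documents do not support them.

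- A reader might infer that the plan misses its 80% under its own assumptions. It does not: full Holm gives 80.5% for high versus low in the expected pattern, and more in some others (83.8% for 0/0.4/1.0). The shortfall of about 2 points appears when two arms are equal and the third differs by only 0.6, whereas the protocol expects at least 0.8 for high dose versus placebo. The protocol's wording on pairwise differences does not exclude such patterns, but with normal tests the figure is 78.7%, close to rounding for a planning number. In 0/0.3/0.6 the largest contrast stays below 80% even with Shaffer's steps, so that shortfall does not come from ignoring the logical link.
- A reader might infer that high-versus-low power falls below 80% when the low dose equals the high dose. In that case the high-versus-low null is true and has no power to lose. The 78% belongs to the two placebo contrasts.

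It is also fair to object that a more permissive rule must not be adopted after results are known. The SAP is written in the past tense and reports findings, so timing matters.

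**Conclusion.** The point holds as a free improvement. Holm is valid and meets the stated 80% in the expected pattern, but Shaffer's steps are never worse and keep strong 5% control. At 53 per arm the gain for high versus low is about 5 points in the expected pattern. It is 4 points for each true 0.6 difference when two arms are equal. It is under 1 point for the largest contrast in 0/0.3/0.6, and about 3 points in the expected pattern at 66 per arm. About 5 points is thus the top of the range for a contrast of d = 0.6, not a general figure.

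The sizes rest on a common SD, normal change scores and a low-versus-placebo effect of 0.2 that is derived, not stated. The error-control argument needs none of those effect sizes, but it covers the three contrasts at one outcome and one time point only. The primary test is unaffected.

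**What to change.** In protocol section IV.F (Sample size justification and Analysis plan), replace plain Holm for the three pairwise contrasts within each outcome and time point with Shaffer's steps: reject the smallest p-value if it is at most 0.0167, then test the other two in order, each at 0.05, stopping at the first that fails. Keep Holm across secondary outcomes. State the pairwise power with its assumed means: about 86% for high versus low under 0/0.2/0.8 with 53 per group. The SAP names no adjustment, so it should cite the same rule and not leave the method to be inferred.

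The cost is a few sentences, with no extra subjects and no loss of error control, provided the change is prespecified before unblinding. If treatment results have already been seen, keep Holm as the reported rule and label any Shaffer analysis as post hoc.
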